		Figure 12.2-1	Updated Addition of Medications Algorithm	To ensure patient safety
		13.1.1.1	Corrected null and alternate hypothesis	To ensure consistency within the protocol
		14.3 / 14.3.4	Added central laboratory	To allow for central analysis of selected serum assessments

Revision History

Revision Number	Release Date	Section	Change	Reason for Change
AC	14-Jan-2016	Synopsis / 8.1	Increase number of centers to 20	To help facilitate timely enrollment
		Synopsis / 7.3	Update Additional Assessments	To ensure consistency with changes to Medication Addition Algorithm
		Synopsis / 11.10 / 12.2	Updated Medication Addition Process	To clarify intent of protocol
		Figure 8.1-1	Updated Study Design Figure	To allow an ABPM one time optional rescreen
		11.5.1 Table 11.18-1	Removed Timeline Requirement	To ensure consistent assessment windows
		12.2	Added Laboratory Source Documentation Requirements	To document data disposition
			Updated Medication Addition Process	To allow investigator discretion when prescribing anti-hypertensive medications
AD	10-Jan-2018	N/A	N/A	Changes proposed to FDA, not approved/not implemented.
AE/AF	N/A	N/A	N/A	Document control system administrative changes only. No content changes.
AG	29-Oct-2018	N/A	N/A	Changes proposed to FDA, not approved/not implemented.

Revision History

Revision Number	Release Date	Section	Change	Reason for Change
AH	23-Jan-2019	Contact Information	Update sponsor contact	Reflect current study contact
		Synopsis / 9.1 / 12.1 / Table 12.1-1 / 12.14-12.17	Updated minimum follow-up visit/assessment requirements to 24 months and added DUS at 24 months	To reduce subject and site effort and collect only the necessary data post enrollment termination of pilot study to ensure subject safety
		Synopsis / 14.1	Updated statistical methods with removal of the primary efficacy statistical hypothesis testing	Due to enrollment termination, insufficient power to make a statistically meaningful conclusion.
		19.4 /19.4.1 / 26.0	Updated confidentiality language	To ensure consistent with current requirements

3. Protocol Synopsis

REDUCE-HTN: REINFORCE	
Objective(s)	To assess safety and efficacy of the Vessix™ Renal Denervation System for the treatment of uncontrolled hypertension [off-treatment office systolic blood pressure (OSBP) ≥ 150 mmHg and ≤ 180 mmHg]
Test Device	Vessix Renal Denervation System: 
 • Vessix Reduce™ Catheter (4.0, 5.0, 6.0 and 7.0 mm) • Vessix™ Generator (bipolar radio frequency)
Control Therapy	Masked procedure (renal angiogram)
Device Sizes	The Vessix Reduce Catheter is available in balloon diameters of 4.0 mm, 5.0 mm, 6.0 mm and 7.0 mm with a balloon length of 25 mm and a total catheter working length of approximately 90 cm. The number of electrodes on each balloon varies from 4 to 6 bipolar electrodes, depending on balloon diameter. The catheter is compatible with a 7F guide sheath.
Study Design	Prospective, multicenter, single blinded, randomized, controlled, pilot study
Planned Number of Subjects	Up to 100 randomized subjects
Planned Number of Centers / Countries	Up to 20 centers in the US
Primary Efficacy Assessment	Mean reduction in average 24-hour ambulatory systolic blood pressure (ASBP) at 8 weeks post randomization Due to enrollment termination (51 subjects randomized), the primary efficacy statistical hypothesis testing will not be conducted. All assessments will be observational.
Safety Assessments	Safety Assessments analyzed at all follow-up time points: 
 • All-cause death • Renal failure • Hospitalization for hypertensive crisis • Hospitalization due to severe hypotension/syncope

REDUCE-HTN: REINFORCE	
	
Safety Assessments analyzed at 4 weeks:
 
 • Significant embolic event resulting in end-organ damage or intervention to prevent it • Renal artery dissection or perforation requiring intervention • Vascular complications requiring surgical repair, interventional procedure, thrombin injection, or blood transfusion 
Safety Assessments analyzed at 6 months:
 
 • Significant new renal artery stenosis assessed by duplex ultrasound (DUS) and confirmed by the angiographic core laboratory [$>70\%$ stenosis by computed tomographic angiography (CTA) or digital subtraction angiography (DSA)] through 6 months post randomization 
Note: All Safety Assessments will be adjudicated by an independent Clinical Events Committee (CEC).

Additional Assessments	
Additional Assessments analyzed at all follow-up time points:
 
 • Mean reduction in office-based systolic blood pressure (OSBP) from baseline • Mean reduction in office-based diastolic blood pressure (ODBP) from baseline • Percent of subjects at target blood pressure • Episodes of Congestive Heart Failure (CHF) • Stroke • Myocardial Infarction (MI) 
Additional Assessments analyzed at 3 and 6 months:
 
 • Anti-hypertensive medications 
Additional Assessments analyzed at 6 and 12 months:
 
 • Mean reduction in average 24-hour ambulatory systolic blood pressure (ASBP) from baseline • Mean reduction in average 24-hour ambulatory diastolic blood pressure (ADBP) from baseline
Randomization	
2:1 (Test:Control)
 
 • Test: Renal Denervation • Control: Masked Procedure (renal angiogram)

REDUCE-HTN: REINFORCE	
Method of Assigning Patients to Treatment	Subjects meeting the eligibility criteria will be randomized at index procedure using an Interactive Randomization System
Follow-up Schedule	
All enrolled subjects will be evaluated at 2 (14 ±7 days), 4 (28 ±7 days) and 8 (56±7 days) weeks post randomization.
 
Subjects will be further evaluated at 3 (90±14 days), 4 (120 ±14 days), 5 (150 ±14 days), 6 (180 ±14 days), 12 (365 ±30 days), 18 (545 ±30 days), 24 (730±30 days), 30 (910±30 days), and 36 (1095 ±30 days) months post randomization.
 
All subjects are required to complete follow up through the 24-month time point. After approval of protocol version AH, no further follow up will be required for subjects who have completed at least 24 months of follow up post randomization. Subjects not yet through the 24-month follow up time point will be required to complete follow up through the 24-month visit and will undergo a DUS at the 24-month follow up time point.

Study Duration	It is estimated that it will take approximately 4 years to complete this study.
Medication Wash-out Phase and Medication Additions	
After signing the study Informed Consent Form, patients receiving pharmacotherapy for their hypertension will be discontinued from current antihypertensive medications. These patients will be required to complete a 4-week wash-out phase prior to randomization. If a patient is not on antihypertensive medication at the time of Informed Consent, the wash-out period is not applicable.
 
Subjects will remain off antihypertensive medications through the primary efficacy assessment (8 weeks post randomization) unless rescue changes are required. Investigators have ultimate discretion regarding the type of antihypertensive medication and timing of adding rescue medications to ensure subject safety.
 
If subjects are not at target (target defined as OSBP <140 mmHg) from the time of the primary efficacy assessment (8 weeks post randomization) through the 6-month assessment, medications will be added and doses escalated as described in Section 13.3.

Key Inclusion Criteria	
 • Age ≥18 and ≤75 years

REDUCE-HTN: REINFORCE	
	
 • OSBP ≥ 150 mmHg and ≤ 180 mmHg based on an average of 3 office-based blood pressure measurements • Average 24-hour ASBP ≥ 135 mmHg and ≤ 170 mmHg • For each kidney, a main renal artery, with or without accessory renal arteries, with diameter ≥ 3.0 mm and ≤ 7.0 mm and length ≥ 20.0 mm • Agrees to have all study procedures performed, and is competent and willing to provide written, informed consent
Key Exclusion Criteria	
 • Previous renal artery intervention or clinically significant renal artery abnormalities that would interfere with safe cannulation of the renal artery • Stenosis $>30\%$ or renal artery aneurysm in either renal artery • Fibromuscular dysplasia (FMD) • Platelet count of $<90,000$ or $>500,000$ per microliter (μL) of blood or history of bleeding diathesis • Known causes of secondary HTN • Type 1 diabetes mellitus • eGFR <40 mL/min/1.73m², as calculated using the MDRD (Modification of Diet in Renal Disease) methodology¹ • Only one kidney or prior transplantation • Contraindicated for anticoagulant therapy and other recommended study medications • Known hypersensitivity or contraindication to contrast dye that, in the opinion of the investigator, cannot be adequately pre-medicated • Pregnant or planning to become pregnant • History of myocardial infarction (MI), unstable angina pectoris, hypertensive crisis, or a cerebrovascular accident (CVA) in the previous 3 months • Known ejection fraction of $<30\%$ or heart failure that required hospitalization in the previous 6 months • Scheduled for or has planned surgery or cardiovascular (CV) intervention in the next 6 months

REDUCE-HTN: REINFORCE	
	
• ≥ 1 episode(s) of orthostatic hypotension not related to medication changes, coupled with symptoms, within the past year or identified during screening• Severe valvular heart disease• History of any serious medical condition, which in the opinion of the investigator, may adversely affect the safety of the participant and/or the scientific integrity of the study• Active implantable device [e.g., implantable cardioverter-defibrillator (ICD), cardiac resynchronization therapy defibrillator (CRT-D), spinal cord stimulators, cochlear implants]• Current participation in another drug or device trial
Multiple Interventions During Index Procedure	There are no concomitant procedures allowed immediately prior to or during the renal denervation procedure.
Statistical Methods	Due to enrollment termination (51 subjects randomized), the primary efficacy statistical hypothesis testing will not be conducted. Descriptive analysis will be performed for data review purposes.

4. Table of Contents

1. TITLE PAGE	1
2. REVISION HISTORY	3
3. PROTOCOL SYNOPSIS	6
4. TABLE OF CONTENTS	11
Table of Figures	16
Table of Tables	16
5. INTRODUCTION	17

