All subjects will be followed at 2 weeks and 1, 3, 6, 12, 18 and 24 months. Follow-up assessments will include office blood pressure measurement, blood assays and urinalysis for renal function, renal DUS at 6 months, and ambulatory blood pressure monitoring (ABPM) at 6 and 12-months. Subjects are required to maintain compliance with all antihypertensive medications throughout the follow-up period.

At 6 months, the mean office SBP was 157.5 ± 23.5 mmHg, a reduction of 24.7 ± 22.1 mmHg compared with baseline ($P < .0001$), thus met the efficacy primary endpoint for the study. Twenty four-hour ambulatory SBP was reduced by 8.4 ± 14.4 mmHg at 6 months ($P < .0001$). No pre-specified acute safety events occurred. However, one subject (0.7%) was hospitalized for a hypertensive emergency unrelated to medication and/or non-compliance within 1 month of the procedure. One subject (0.7%) had renal artery stenosis which required an intervention. Three other subjects had flow-limiting stenosis in the renal artery at 6 months which did not require intervention. ¹⁴

Subject follow-up in the REDUCE-HTN Study continues and data monitoring activities are ongoing through 2 years post procedure.

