After the primary endpoint was met, 46 control patients (cross over group) underwent renal denervation. Esler et al¹⁷ [ENREF 18](#) reported that the 6-month follow up of the cross over group showed a significant drop in blood pressure (190.0/99.9 mmHg to 166.3/91.5 mmHg). The one-year follow-up of the initial RDN group continued to show significantly lower blood pressure when compared to baseline office BP; although BP at 12 months was slightly elevated from the 6-month average (-31.7/-11.7 at 6 months compared to -28.1/-9.7 at 12 months).

As with HTN-1, a favorable safety profile was observed in HTN-2. Safety outcomes for HTN-2 demonstrated no serious procedure or device related complications or elevated occurrence rates of adverse events. In the treatment group, one subject had a possible progression of an underlying atherosclerotic lesion but required no further treatment.

The Simplicity HTN-3¹⁸ trial is a pivotal study designed as a prospective, randomized, masked procedure, single-blind trial evaluating the safety and effectiveness of catheter-based bilateral renal denervation for the treatment of resistant hypertension despite compliance with at least 3 antihypertensive medications of different classes at maximal tolerable doses. Bhatt et al¹⁹ report 535 patients were enrolled into the trial; 2 treatment : 1 control (masked procedure). The primary efficacy endpoint of mean change at 6 months in systolic office blood pressure was not met. The reduction for the treatment group was -14.13±23.93 mmHg and for the control was -11.74±25.94 mmHg; P=0.26. The study continued to demonstrate safety of the technology with a 1.4% major adverse event rate for the renal denervation group and 0.6% for the masked procedure group. Ongoing discussions continue as to why these results do not replicate those of previous trials. Medication compliance and adjustments are thought to have played a role.²⁰

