14.2.2. Randomization Scheme

Randomization to treatment will be stratified by study site. A computer generated list of random treatment allocations (i.e., a randomization schedule) will be used to assign subjects to treatments in a 2:1 ratio of Test to Control. This list will be specific to the subject's site. Random permuted blocks of varying sizes will be employed to ensure approximate balance of treatment allocation within each site.

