14.3. Data Analyses

Baseline data will be summarized by treatment group for the randomized study. Subject demographics, clinical history, procedure assessment, and medication compliance will be summarized using descriptive statistics (e.g., mean, standard deviation, n, minimum, maximum) for continuous variables and frequency tables for discrete variables. The analysis unit may be (but will not be limited to) by subject, catheter, or treatment.

Test and Control in the randomized study will be compared as needed with a Chi-square test or a Fisher exact test for discrete variables and a Student t-Test for continuous variables. The differences between Test and Control in the randomized study and their 95% confidence intervals will be presented as needed.

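### With 2:1 allocation, the Student t-test named in section 14.3 gives true 95% intervals only if the two arms have equal SDs; naming the Welch form removes that dependence at almost no cost

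*Combined protocol and SAP*

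**What the plan says.** - **Allocation.** The Synopsis gives "2:1 (Test:Control". Section 14.2.2 repeats that a computer-generated list will "assign subjects to treatments in a 2:1 ratio of Test to Control", stratified by site in permuted blocks.
- **Size.** The Synopsis planned "Up to 100 randomized subjects", but recruitment stopped early: "Due to enrollment termination (51 subjects randomized". The number in each arm is not given.
- **Method.** Section 14.3 says the arms are compared as needed, with "a Student t-Test for continuous variables". Its next sentence reads: "The differences between Test and Control in the randomized study and their 95% confidence intervals will be presented as needed". It gives no variance assumption, interval formula or unequal-variance alternative.
- **Status.** Section 14.1.1 withdraws formal hypothesis tests for the primary assessment, and section 14.3.1 treats comparisons of the additional assessments as exploratory.
- **SDs cited.** Section 5.2.1.1 reports a 2:1 masked-procedure trial with office systolic pressure at 6 months: "The reduction for the treatment group was -14.13±23.93 mmHg and for the control was -11.74±25.94 mmHg". For ambulatory pressure, the only SD is from the sponsor's earlier single-arm study (section 5.2.1): "Twenty four-hour ambulatory SBP was reduced by 8.4 ± 14.4 mmHg at 6 months".

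**The concern.** Student's t-test estimates one common variance and uses it for both arms. When the arms are the same size this does little harm even if the variances differ. When one arm is twice the size of the other, the pooled estimate is dominated by the large arm, while the uncertainty of the difference is dominated by the small one. If Control (the small arm) is more variable, the interval is too narrow. If Test is more variable, it is too wide.

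The protocol gives no basis for assuming equal spread. Rescue medication before week 8 (section 13.1) or uneven response to denervation could make the arms differ, in either direction. With formal testing withdrawn, a reader will look to the estimated Test-minus-Control difference and its interval. An interval labelled 95% should have that coverage.

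**Working it through.** The plan states no power, design SD or interval width for this comparison, so there is no figure of its own to reproduce. The check compares the pooled interval with its true behaviour.

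**Inputs.** n = 51 (Synopsis) and 2:1 allocation (Synopsis, 14.2.2), giving an assumed n₁ = 34 Test and n₂ = 17 Control. SDs of 23.93 and 25.94 are from section 5.2.1.1, and 14.4 from section 5.2.1. SD ratios of 1.25 and 1.5 are assumptions.

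**Formulas.**
- Pooled SE = √{[(33s₁² + 16s₂²)/49] × (1/34 + 1/17)}, with 49 df.
- True SE = √(s₁²/34 + s₂²/17). Welch puts the sample SDs into this, with Satterthwaite df.

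Written as weights, pooled SE² is 0.0594 s₁² + 0.0288 s₂², whereas the true value is 0.0294 s₁² + 0.0588 s₂². Pooling nearly exchanges the weights of the two arms, and this is harmless only if s₁ = s₂.

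**At the cited SDs.**
- Pooled variance = (33 × 572.64 + 16 × 672.88)/49 = 605.4, so the pooled SD is 24.60 and the pooled SE is 24.60 × 0.2970 = 7.31.
- True SE = √(16.84 + 39.58) = 7.51. The ratio is 7.31/7.51 = 0.973, so the pooled SE is 2.7% too small.
- Half-widths with these SDs as observed: pooled 2.010 × 7.309 = 14.69 mmHg; Welch (29.9 df) 2.043 × 7.512 = 15.34 mmHg. The pooled interval is about 4% narrower.
- On the ambulatory scale, assuming SDs of 14.4 and 15.6 (the same ratio), the half-widths are 8.84 and 9.23 mmHg.

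**Coverage of nominal 95% intervals at 34/17**, from simulated sample variances under normality:

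| SDs | Pooled SE / true SE | Pooled coverage | Welch coverage |
|---|---|---|---|
| Equal | 1.000 | 95.0% | 95.0% |
| 23.93 Test, 25.94 Control (cited) | 0.973 | 94.4% | 95.0% |
| Control 1.25 × Test (assumed) | 0.928 | 93.2% | 95.0% |
| Control 1.5 × Test (assumed) | 0.876 | 91.5% | 95.0% |
| Test 1.25 × Control (assumed) | 1.078 | 96.5% | 95.0% |
| Test 1.5 × Control (assumed) | 1.140 | 97.3% | 95.0% |

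**Role of the allocation.** With a near-equal split (25/26), pooled coverage stays between 94.5% and 95.1% for SD ratios up to 2. The sensitivity comes from the 2:1 ratio.

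**Are the cited SDs evidence of a difference?** F = (25.94/23.93)² = 1.175. Taking the cited trial's 535 patients as about 357 and 178 (assumed), two-sided p is about 0.21, and the 95% interval for the Control/Test SD ratio is about 0.96 to 1.24. Equality is not excluded.

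**Price of Welch when the SDs are equal.** At SD 14.4 the average half-width is 8.65 against 8.55 mmHg: 8.65/8.55 = 1.012, or 1.2% wider.

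**The case against.** The strongest reply is that the loss at the only figures in the documents is 0.6 percentage points, and that everything larger rests on assumed SD ratios. That stands, and it limits the size of the point.

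A reader might infer from section 5.2.1.1 that the interval here will be too narrow. The documents do not support that. Those SDs are for office pressure at 6 months in resistant hypertension on at least three drugs, whereas the primary measure here is 24-hour ambulatory pressure at 8 weeks off medication. The two SDs are also compatible with equality. Mixed response to denervation would push the other way.

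A reader might also infer that the planned intervals are simply wrong, or that the efficacy conclusion depends on them. Neither follows. With equal SDs, pooled coverage is exactly nominal under normality. The plan calls its analyses observational and descriptive, and no decision rule uses a confidence limit.

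Finally, 14.3 does not say that variances are pooled, gives the test and the intervals in separate sentences, and makes both conditional on need. Sections 14.3.2 and 14.3.5 refer to a Statistical Analysis Plan whose detailed methods are not in the text available, so it may specify the interval. This is fair, but Student's test is conventionally the pooled one. Neither the reference to a SAP nor the descriptive status removes the 95% intervals from 14.3.

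**Conclusion.** The point holds as a cheap improvement. On its conventional reading, the method named in 14.3 gives 95% coverage under 2:1 allocation only if the arms' SDs are equal, and the plan offers no ground for that assumption. The shortfall is 0.6 points at the cited SDs. Over assumed ratios of 1.25 to 1.5, coverage is 93.2% to 91.5% with Control more variable, or 96.5% to 97.3% with Test more variable. Which case applies to 8-week ambulatory pressure is unknown. These figures assume a 34/17 split, normal data and a pooled interval. The consequence is confined to the accuracy of the reported intervals.

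**What to change.** In section 14.3 and the SAP, replace the Student t-test with the Welch unequal-variance t-test. State that 95% intervals for continuous Test-minus-Control differences use the unequal-variance standard error with Satterthwaite degrees of freedom. Section 14.3.5 already provides the route: an amended SAP approved before the analyses are run.

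The change is one phrase and needs no new data. Its only downside is an interval about 1.2% wider (roughly 0.1 mmHg on the half-width at SD 14.4) if the SDs turn out equal.

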As early as the 1930s, surgical procedures of splanchnicectomy and radical sympathectomy were conducted to reduce blood pressure in patients. This research demonstrated that procedures targeted at reducing sympathetic nerve activity achieved blood pressure reductions in the treated patients, demonstrating improved long-term outcomes.^{7,8} However, these methods were abandoned because they were associated with high perioperative morbidity and mortality and long-term complications.^{2,3,8,9} Radio frequency⁹ current has been used for decades in the operating room to safely and effectively create surgical lesions and to facilitate hemostasis.^{10,11} The technique of catheter based RF ablation to treat arrhythmias was developed as an adaptation of electrosurgical cautery.

In the late 1990s, the connection between hypertension and the sympathetic nervous system, specifically the renal nerves, was reconfirmed. [ENREF 12](#) Shortly thereafter, catheter-based RF ablation was applied to renal nerves as a hypertension treatment.¹² Clinical evidence continues to confirm that the renal efferent sympathetic nerves and afferent sensory nerves that lie within and immediately adjacent to the wall of the renal artery are crucial for initiation and maintenance of systemic hypertension.^{2,3,12} Renal sympathetic efferent nerve activity participates in renin release, sodium retention and reduced blood flow which in turn, contributes to the development and maintenance of hypertension.⁴ Renal sympathetic afferents are recognized as seminal in conveying central sympathetic drive in patients with both chronic kidney disease and end-stage renal disease.⁴ Thus, inhibition of the renal sympathetic efferent or afferent nerves (or both) represents an attractive treatment of established hypertension.

Today, despite the availability of numerous antihypertensive drugs, dietary and lifestyle changes, hypertension remains an issue in a considerable number of patients. New innovative therapeutic approaches such as renal nerve ablation may be particularly relevant for these patients as their hypertensive state puts them at high risk of major cardiovascular events.² A recent article by Kostis et al. reported that in hypertensive patients being treated by medication, each month of active treatment was associated with approximately 1 day of life expectancy gain.¹³ Renal ablation has the potential to provide a long term effect on hypertension which could increase the patient's life expectancy and reduce the economic burden of a progressive disease state.

